An interim analysis of effectiveness will be performed when there are at least 25 laboratory-confirmed COVID-19 cases observed among the study participants. If the assumptions made in the power calculations are correct (COVID-19 rate is 0.05 in the placebo group and 0.01 in the NTZ group) we expect to observe only 24 events during the entire study. If this milestone is reached early, it indicates that the assumptions were

conservative and merit review given the high rate of mortality observed from COVID-19 illness in this population. This review will be conducted by the IDMC in accordance with its charter and will encompass both a safety and efficacy determination. In the event that the timing of the interim analysis of effectiveness is near that of the second review for safety and futility, analyses of safety, futility and effectiveness may be performed simultaneously.

O'Brien-Fleming bounds are used to set the Type I error rates for the third interim and final analyses. The interim efficacy review will be performed with  $\alpha = 0.0052$  (overall), allocated 0.005 to the COVID-19 endpoint and 0.0002 to the VRI endpoint. The final data analysis (if the efficacy hypotheses are not rejected at the interim review) will be performed with  $\alpha = 0.048$ , allocated 0.047 to the COVID-19 endpoint and 0.001 to the VRI endpoint. Power at the interim analysis is 31% for the COVID-19 endpoint. If the interim review for efficacy does not occur (i.e., the event count of 25 is not reached or reached too late in the study for the interim review to be useful), the alpha levels for the final analysis will be 0.049 for the COVID-19 endpoint and 0.001 for the VRI endpoint.

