## 4.2 Efficacy Analysis

### 4.2.1 Primary Efficacy Variables

The study has two primary efficacy endpoints: reduction in symptomatic COVID-19 disease and reduction in all VRI. The study-wise  $\alpha$  level is set at 0.05, allocated with 0.049 to the COVID-19 endpoint and 0.001 to the all VRI endpoint. See Section 2.4 for details on how the study- wise  $\alpha$  level will be allocated to the interim and final analyses. For each endpoint, the following hypotheses will be tested

$$H_0: p_1 = p_2$$

$$H_1: p_1 \neq p_2,$$

here,  $p_1$  represents the probability of symptomatic disease (either COVID-19 or VRI) in the NTZ treatment group and  $p_2$  represents the probability of symptomatic disease in the placebo group.

The proportion of subjects experiencing symptomatic COVID-19 disease in the NTZ treatment group will be compared to the similar proportion in the placebo group using a two-sided CMH test with continuity correction at  $\alpha=0.047$ . The test will be stratified by LTCF. The contingency tables will be provided with rates relative to the treatment margins. A 95% confidence interval for the odds ratio of symptomatic COVID-19 infection in the NTZ group relative to the placebo group will be provided. The risk difference for the treatment groups and a 95% confidence interval for the difference will be provided.

The proportion of subjects experiencing symptomatic VRI infections in the NTZ treatment group will be compared to the similar proportion in the placebo group using a two-sided CMH test, stratified by LTCF with continuity correction at  $\alpha=0.001$ . The contingency tables will be provided with rates relative to the treatment margins. A 95% confidence interval for the odds ratio of symptomatic VRI in the NTZ group relative to the placebo group will be provided. The risk difference for the treatment groups and a 95% confidence interval for the difference will be provided.

CMH analyses of symptomatic COVID-19 disease and symptomatic VRI will be repeated with subjects divided by sex (female or male), age (65- to 79 years or 80 years and over), and race (white or non-white). Estimates and confidence intervals for the odds ratio and relative risk differences will be provided.

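### The interim and final alpha levels in SAP 2.4 do not add up to the endpoint allocations: VRI is not charged for its interim look, COVID-19 levels assume half information at a case-triggered look, and 4.2.1 prints 0.047 without the condition

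*SAP*

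**What the plan says.** SAP 4.2.1 sets a study-wise alpha of 0.05, "allocated with 0.049 to the COVID-19 endpoint and 0.001 to the all VRI endpoint", and refers to 2.4 for the division between interim and final analyses. The sentence describing the COVID-19 test then gives 0.047, and the one describing the VRI test gives 0.001, neither with a condition.

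SAP 2.4 says of the O'Brien-Fleming method that its "bounds are used to set the Type I error rates for the third interim and final analyses". The levels are:

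- Efficacy interim: 0.0052 overall, "allocated 0.005 to the COVID-19 endpoint and 0.0002 to the VRI endpoint".
- Final analysis after that interim: 0.048 overall, "allocated 0.047 to the COVID-19 endpoint and 0.001 to the VRI endpoint".
- No efficacy interim, or 25 cases reached too late for the review to be useful: "the alpha levels for the final analysis will be 0.049 for the COVID-19 endpoint and 0.001 for the VRI endpoint".

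The timing is set by a case count: "An interim analysis of effectiveness will be performed when there are at least 25 laboratory-confirmed COVID-19 cases observed among the study participants". Under the planning rates, "we expect to observe only 24 events during the entire study". No information fraction is stated, and no rule recalculates the levels at the actual timing. Protocol 8.4.1 uses 0.049 and 0.001.

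**The concern.** Three things do not fit together.

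1. The final VRI level is 0.001 whether or not 0.0002 was used at the interim. COVID-19, by contrast, drops from 0.049 to 0.047. So the interim VRI test is not paid for.
2. A fixed O'Brien-Fleming pair belongs to one information fraction. A look triggered by 25 cases can fall anywhere, and it falls early when the attack rate is high, which is the situation the look was written for.
3. The final COVID-19 threshold appears as 0.047 in 4.2.1, and as 0.047 or 0.049 in 2.4. A p-value between the two would be read differently depending on which sentence is followed.

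At stake are exact endpoint allocations and an unambiguous final decision threshold. Both should be settled before unblinding.

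**Working it through.** **Inputs.** Allocations 0.049 and 0.001 (SAP 4.2.1); levels 0.005/0.047 and 0.0002/0.001 and the 25-case trigger (SAP 2.4); 400 per arm, 5% vs 1% and 10% vs 2% (SAP 1.3). The information fraction t is not in the documents. It is an assumption here, shown over a range and read where needed as 25 divided by the total number of cases.

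**Formula.** For two looks with corr(Z1, Z2) = √t, the total two-sided error is 1 − P(|Z1| < c1, |Z2| < c2), with c1 and c2 the normal critical values of the nominal levels.

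**Reproducing the plan's figures.** O'Brien-Fleming at t = 0.5 (c1 = c2/√0.5):

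- Total 0.05: 0.00517 / 0.04799. The plan has 0.0052 / 0.048.
- Total 0.049: 0.00498 / 0.04706. The plan has 0.005 / 0.047.
- Total 0.001: 0.0000033 / 0.000999. The plan has 0.0002 / 0.001, which is not this pair.

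The power figures also point to half information. With 200 per arm at 0.005 and no continuity correction: SE0 = √(2×0.03×0.97/200) = 0.01706, SE1 = √((0.05×0.95 + 0.01×0.99)/200) = 0.01694, Φ((0.04 − 2.807×0.01706)/0.01694) = 32.1% (stated 31%). With 400 per arm at 0.047 and continuity correction 1/400: Φ((0.0375 − 1.986×0.01206)/0.01198) = 87.1% (stated 87.1%).

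**Nominal total spent with the printed levels.**

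| t | COVID-19 (0.005, 0.047) | VRI (0.0002, 0.001) |
|---|---|---|
| 0.25 | 0.0505 | 0.00119 |
| 0.3 | 0.0502 | 0.00118 |
| 0.4 | 0.0496 | 0.00117 |
| 0.5 | 0.0490 | 0.00115 |
| 0.6 | 0.0483 | 0.00113 |
| 0.75 | 0.0475 | 0.00108 |
| 0.9 | 0.0470 | 0.00102 |

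VRI is above 0.001 at every t below 1; the simple sum 0.0002 + 0.001 = 0.0012 is the upper bound. COVID-19 crosses 0.049 at t = 0.492. As a case fraction that is 25/0.492 ≈ 51 cases in total, or 51/800 = 6.4% pooled, against a planned 24/800 = 3%. Reaching t = 0.3 takes 25/0.3 ≈ 83 cases, about 10% pooled.

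**Both endpoints together.** The sum at t = 0.5 is 0.04895 + 0.00115 = 0.0501. The tests are correlated because COVID-19 is a subset of VRI; from the placebo planning rates ρ = √(0.05×0.90/(0.10×0.95)) = 0.69. Simulated nominal family-wise error is then 0.0508 at t = 0.25, 0.0492 at t = 0.5 and 0.0478 at t = 0.75. With independent tests it is 0.0516, 0.0500 and 0.0485.

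**Final levels that hold the allocations after 0.005 and 0.0002.** COVID-19: 0.0458 at t = 0.3, 0.0464 at 0.4, 0.0471 at 0.5, 0.0477 at 0.6. VRI: 0.00082 at t = 0.3, 0.00085 at 0.5, 0.00094 at 0.8.

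**The 0.047/0.049 wording.** Using 0.047 with no interim gives 87.1% power, against Φ((0.0375 − 1.969×0.01206)/0.01198) = 87.5% at 0.049: a cost of about 0.4 points and no added error. The case is not rare. With cases distributed as Bin(400, 0.05) + Bin(400, 0.01), the chance of reaching 25 is 0.446, so about 55% of trials under the planning rates would have no efficacy interim.

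**The case against.** The best defence is that no real error inflation has been shown. SAP 4.2.1 specifies a CMH test stratified by LTCF with continuity correction, and that test is conservative with sparse strata. Null simulations of it (assuming 20 equal LTCFs, 400 per arm and the same corrected test at both looks) gave total error of 0.027 to 0.041 for COVID-19 and 0.0002 to 0.0009 for VRI, including early looks. Neither allocation was exceeded in any setting run. This stands. It means the point concerns nominal levels, although a plan should not depend on a conservative test to make its stated levels add up.

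Three stronger readings are tempting and are not supported:

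- *That the study-wise 0.05 is broken.* At half information the nominal family-wise error is about 0.049 with correlated endpoints. It passes 0.05 only for clearly early looks.
- *That COVID-19 keeps 0.049 only at exactly half information.* It keeps it at any look from about t = 0.49 onward, with room to spare when the look is late.
- *That 4.2.1 contradicts 2.4 in a way that inflates error.* SAP 4.2.1 states the 0.049 allocation and refers to 2.4, where the conditional rule is explicit and also covers a look that comes too late. The unconditional 0.047 is an inconsistency in the safe direction, and it matters only for p-values between 0.047 and 0.049.

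**Conclusion.** The point holds as a small error in the levels as written.

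- VRI: a nominal total of about 0.00115 against 0.001 at half information, an excess of about 0.00015. The excess exists at any timing before full information and so needs no assumption about t.
- COVID-19: levels correct for half information, attached to a trigger that does not fix the information fraction. The nominal excess arises only for looks before about t = 0.49 and is about 0.001 at t = 0.3 (0.0502 against 0.049).
- SAP 4.2.1: wording to reconcile with 2.4; no inflation.

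The COVID-19 and family-wise figures rest on the two-look normal approximation, on assumed values of t, and (family-wise only) on a correlation of 0.69 derived from the planning rates. The finding that the actual test stays below both allocations rests on the simulated settings.

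**What to change.** In SAP 2.4, set the final level for each endpoint from the alpha actually spent at the interim and the actual information fraction, so that COVID-19 totals 0.049 and VRI totals 0.001. Either route works:

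- Keep 0.005 and 0.0002 at the interim and solve for the final levels (about 0.0471 and 0.00085 at t = 0.5).
- Use a Lan-DeMets spending function for each endpoint, with nothing spent if no efficacy look is made.

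Define information explicitly, for example as the fraction of planned ITT subjects with complete endpoint data. Cases divided by planned cases will not do: 25/24 puts t above 1.

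In SAP 4.2.1, replace the fixed 0.047 and 0.001 by a reference to the final level from Section 2.4, adding that this is 0.049 and 0.001 if no efficacy interim is held.

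The cost is SAP wording and one standard boundary calculation at the interim. The price in the analysis is a slightly stricter final VRI level or, with O'Brien-Fleming-type spending, almost no interim alpha for VRI (about 0.000003 at t = 0.5), which in practice removes the interim VRI test.

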### 1.3 Sample Size

Recent reports of COVID-19 in long-term care facilities in the United States have suggested a high rate of transmission of the SARS-CoV-2 virus, but infection control procedures may significantly decrease transmission (McMichael et al. 2020, Kimball et al. 2020). A recent study of 264 elderly volunteers ( $\geq 65$  years of age) reported 1.6 respiratory tract infections (not laboratory-confirmed) per person-year indicating approximately a 20% probability of respiratory tract infection over a given 6-week period (Mannick et. al, 2018). Infection control procedures in place during the period covered by this clinical trial are also expected to reduce the transmission of other respiratory viruses.

For purposes of calculating sample size, we assume that the proportion of subjects experiencing COVID-19 over a 6-week period is 5%, the proportion of subjects experiencing any VRI is 10%, and that effective prophylaxis will reduce the rate of COVID-19 and other VRIs by 80%.

A Cochran-Mantel-Haenszel (CMH) chi-square test stratifying by 20 LTCFs will have 87.1% statistical power to detect the difference between 5% and 1% rates of occurrence of COVID-19 across all strata at a two-sided alpha of 0.047 with a total sample size of 800, allocated equally to strata (LTCFs) and treatment groups within strata. The statistical

power remains >87% when the number of LTCFs is 5, 10, 16 or 20. The CMH chi-square test has 91% power to detect the difference between 10% and 2% rates of occurrence of VRIs over all strata at a two-sided alpha of 0.001 with 800 subjects allocated equally to 20 LTCFs. Both tests are insensitive to stratum size. Varying the number of subjects per stratum (LTCF) between a minimum of 8 to a maximum of 80 while holding both the effect size and total sample constant results in changes in the third significant figure of the test's power.

A sample size of 800 subjects (400 per treatment group) was selected.

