### 2.2 Analysis Populations

#### 2.2.1 Population Definitions

Subjects will be considered enrolled in the study upon completion of the baseline procedures. The following analysis populations will be used in the study.

- **Safety Population** – the safety population includes all patients who are enrolled in the study and that have received at least one dose of the assigned treatment arm (NTZ or placebo)
- **Intention to Treat Population (ITT)** – the ITT population includes all patients in the safety population who did not have a laboratory detected respiratory virus infection at the baseline visit.

The safety population will be used for all safety analyses. The ITT population will be the primary population for all efficacy analyses.

Data listings displaying the patients excluded from each population will be created. These listings will be relative to all patients enrolled in the study.

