## 4.0 Analysis of Efficacy

### 4.1 Efficacy Variables

The efficacy variables are categorical in nature: the presence or absence of ARI, VRI, or COVID-19 and sequelae during the study period or COVID-19 and sequelae (i.e., hospitalization and death) during the study period.

Symptomatic COVID-19 is defined as an ARI after start of treatment and before the end of the 6-week treatment period associated with detection of SARS-CoV-2 by RT-PCR assay of nasopharyngeal swab.

Symptomatic VRI is defined as an ARI after start of treatment and before the end of the 6-week treatment period associated with detection of any respiratory virus by RT-PCR assay of nasopharyngeal swab.

ARI is defined as  $\geq 0.5$  increase from baseline in mean symptom score in the chest/respiratory domain of the FLU-PRO® instrument; or an increase of at least 0.5 in the mean symptom score of at least two of the following FLU-PRO® domains: body/systemic, nose, throat.

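### SAP 2.4 states 31% COVID-19 power for the efficacy interim, which does not match the 25-case look it describes: about 77% with exactly 25 ITT endpoint events, or 65-71% if 25 is the expected count

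*SAP*

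**What the plan says.** SAP 2.4 performs the effectiveness interim once there are "at least 25 laboratory-confirmed COVID-19 cases observed among the study participants". It notes that under the planning rates "we expect to observe only 24 events during the entire study", so the trigger lies above the planned total. The COVID-19 endpoint is tested at 0.005 at this look and at 0.047 at the final analysis. The same paragraph then states: "Power at the interim analysis is 31% for the COVID-19 endpoint". No number enrolled, number of endpoint events, information fraction, rates or test is attached to that sentence.

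The other ingredients are elsewhere in the SAP:

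- **Effect:** section 1.3 assumes that "effective prophylaxis will reduce the rate of COVID-19 and other VRIs by 80" per cent.
- **Final power:** section 1.3 says the stratified test "will have 87.1% statistical power to detect the difference between 5% and 1% rates of occurrence of COVID-19" at two-sided alpha 0.047 with 800 subjects. It gives 91% for VRI (10% vs 2%, alpha 0.001).
- **Test:** section 4.2.1 compares the arms "using a two-sided CMH test with continuity correction at" the stated level, stratified by facility.
- **Endpoint:** section 4.1 says "Symptomatic COVID-19 is defined as an ARI after start of treatment and before the end of the 6-week treatment period", with SARS-CoV-2 detected by RT-PCR. ARI is defined by FLU-PRO score increases.
- **Population:** under section 2.2.1 the ITT population is limited to treated subjects "who did not have a laboratory detected respiratory virus infection at the baseline visit".

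**The concern.** An interim held at 25 events has at least as many events as the whole study was planned to yield. The final test is said to have 87.1% power with 24 expected events. Moving from alpha 0.047 to 0.005 costs power, but a fall to 31% looks too large.

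The 31% is the only operating characteristic the SAP gives for this look. Taken at face value, it tells the IDMC that the look has about a one-in-three chance of detecting the planned effect, and that a non-rejection says little. If 25 qualifying events are in hand, the chance is much higher and a non-rejection carries more information.

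**Working it through.** **Inputs.** Reduction 80% (risk ratio 0.2), 400 per arm, planning rates 5% and 1% (SAP 1.3); interim alpha 0.005 two-sided and trigger 25 (SAP 2.4); continuity-corrected test (SAP 4.2.1). The number enrolled at the look is not given, so I assume 100 to 400 per arm.

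**Formula.** With n per arm, NTZ rate p1, placebo rate p2 and pbar their mean:

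power = Φ( (p2 − p1 − 1/n − z·√(2·pbar·(1 − pbar)/n)) / √((p1q1 + p2q2)/n) )

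The 1/n term is the continuity correction. The SAP prints no power formula, so this one is inferred from the calibration below.

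**1. Reproduce the SAP's final powers.**

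- COVID-19, n = 400, alpha 0.047 (z = 1.986): (0.04 − 0.0025 − 0.02396)/0.01198 = 1.130, so power is 87.1%. The SAP says 87.1%.
- VRI, n = 400, alpha 0.001 (z = 3.291): (0.08 − 0.0025 − 0.05526)/0.01655 = 1.344, so power is 91.0%. The SAP says 91%.

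**2. Interim with 25 expected endpoint events.** Here p2 = 25/(1.2n), p1 = 0.2·p2 and z = 2.807. For n = 200, p2 = 0.1042 and p1 = 0.0208: (0.08333 − 0.005 − 0.06795)/0.02384 ≈ 0.436, so power is 66.8%.

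| n per arm | corrected | uncorrected |
|---|---|---|
| 100 | 71.3% | 78.3% |
| 200 | 66.8% | 74.1% |
| 300 | 65.5% | 72.7% |
| 400 | 64.8% | 72.0% |

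Simulation of the corrected stratified CMH test with a mean of 25 events gives 68-74%. The SAP's own 24-event scenario (n = 400, 5% vs 1%) at alpha 0.005 gives (0.04 − 0.0025 − 0.03386)/0.01198 = 0.304, or 62%.

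**3. Interim with exactly 25 endpoint events.** The trigger is a count, so this is the closer description. With 1:1 allocation and risk ratio 0.2, each event falls in the NTZ arm with probability 0.2/1.2 = 1/6. A 5 vs 20 split gives corrected p = 0.0028 (100 per arm) to 0.0045 (400 per arm) and rejects. A 6 vs 19 split gives 0.0105 to 0.0148 and does not. Power is therefore P(X ≤ 5) for X ~ Bin(25, 1/6), which is 77.2%. Stratified simulation also gives 77%. The 5 vs 20 split is close to the boundary: a corrected binomial test on the 25 events would just fail to reject there and gives 59%, still far above 31%.

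**4. If fewer of the 25 cases qualify.**

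| endpoint events | largest NTZ count that rejects | power |
|---|---|---|
| 25 | 5 | 77% |
| 20 | 3 | 57% |
| 18 | 2 | 40% |
| 15 | 1 | 26% |

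**5. What would give 31%.** At an 80% reduction, the corrected formula needs 14.1 (n = 100) to 14.7 (n = 400) expected events. At 25 expected events, it needs a risk ratio of 0.357 to 0.337, a reduction of 64-66%. The SAP states neither.

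**6. Possible source.** At 200 per arm and 5% vs 1% there are 200 × 0.06 = 12 expected events. The uncorrected formula gives (0.04 − 0.04788)/0.01694 = −0.465, or 32%. The corrected one gives (0.04 − 0.005 − 0.04788)/0.01694 = −0.760, or 22%. Two-look O'Brien-Fleming levels for 0.049 at 50% information are 0.00498 and 0.0471, which match the SAP's 0.005 and 0.047.

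**The case against.** The best defence is that the SAP never ties the 31% to 25 endpoint events with an 80% reduction. It leaves the basis unstated, and the figure may be roughly right for a half-information look: the alpha levels fit one, and SAP 2.4 allows that the efficacy interim may fall near the 50% review. This stands as a likely origin, but it remains an inference. The sentence appears in the paragraph on the 25-case look, and a reader will apply it there.

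A second defence is that the trigger counts laboratory-confirmed cases among participants, not ITT endpoint events. This stands as a condition on every figure above. To bring power down to 31%, about 10 of the 25 cases would have to fail to qualify (25 − 14.7 = 10.3 by the formula). The SAP assumes no such loss and itself sets the 25 against the 24 planned events.

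A third defence is that 31% could be the joint chance of reaching 25 events and then rejecting. At 5% vs 1%, 25 or more events occur in about 45% of full-size trials, giving 0.447 × 0.648 = 29% or 0.447 × 0.772 = 35%. The number is close, but the SAP describes power at the analysis, and this reading would place the look at about the end of the study.

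A reader might infer more than this: that the trigger, the alpha levels or error control are unsound, or that interim power is definitely two-thirds or more. The documents do not support either inference. The 31% enters no stopping rule, and no document gives the fraction of trigger cases that would qualify as endpoint events.

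**Conclusion.** The stated 31% does not match the look described in SAP 2.4. With an 80% reduction, alpha 0.005, the two-sided corrected test and all 25 cases counting as ITT endpoint events, power is about 77% at exactly 25 events. It is 65-71% if 25 is the expected count. The assumed enrolment matters little: a fourfold range moves the second figure by about 6 points. The share of cases that qualify matters more, with power falling to 57%, 40% or 26% at 20, 18 or 15 events. No variant tried gives 31% with 25 endpoint events and an 80% reduction. This is a minor correction of a reported operating characteristic. Trigger, COVID-19 alpha levels, sample size and final analysis are unaffected.

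**What to change.** In SAP 2.4, replace 31% with the power at the 25-case trigger: about 77% for exactly 25 ITT endpoint events, or about 65-71% if 25 is treated as the expected count. State the assumptions beside it: effect size, alpha, test, number of qualifying endpoint events and number enrolled at the look. If 31% was meant for a half-information look, say so, give that look's sample size, rates and test, and report the power at the trigger separately.

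The cost is one recalculation and a sentence or two of text. Nothing in the design or the data changes.
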